- Afterward, a proper physical examination will be performed including a thorough clinical examination of the oropharynx, nasopharynx, and hypopharynx to evaluate any anatomical abnormalities as impotency of the nasal airway, elongated soft palate or uvula, enlarged lingual tonsils, and any other pathological conditions of tongue, palate, and tonsils.
- Then, Polysomnography (PSG) (sleep study) will be performed to allow proper evaluation of normal and abnormal physiological sleep episodes. Apnea/Hypopnea Index (AHI) will be reported to detect the severity of OSA and patients were classified into mild (AHI = 5-14 / hour), moderate (AHI = 15-30 / hour) and severe (AHI >30 / hour) (*Maspero et al. 2015*).
- All patients in both groups will undergo upper airway surgery, DISE will be performed by the same ENT surgeon to detect the level of collapse in the upper airway which will be assessed by LwPTL and VOTE classifications, emphasizing on the primary structures contributing at upper airway collapse, either alone or in combination: the larynx, palate, tongue and pharyngeal lateral walls.
- Study group participants only will be scanned by CBCT twice; once at the end of inspiration and the other at the end of expiration while they are gently holding their breath for as long as possible. (*Woodson 2003*)
- In the study group, surgical procedures decision will be taken after appropriate assessment to sites of collapse in CBCT views at both ends of expiration and inspiration vies in combination to DISE.
- Finally, strict post-operative instructions will be given to patients of both groups.

2. Settings

This study will be carried out on patients attending outpatient clinics in the ENT department, Faculty of Medicine, Mansoura University, Egypt. CBCT scans of surgical candidates of OSA patients will be included

according to the proposed eligibility criteria.

B) Participants

1. Eligibility criteria and selection methods

Inclusion Criteria:

- Patients' age is more than 18 years old.
- Patients are indicated for upper respiratory airway surgery based on adequate history taking, proper clinical examination, and sleep study.
- Patients refusing non-surgical treatment procedures as Continuous Positive Airway Pressure (CPAP) treatment.
- Systemically medically free patients.

Exclusion Criteria:

- Patients who are refusing the surgical approach as a treatment option.
- Patients who have undergone previous surgeries in the upper respiratory airway.
- Pregnant women.

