- Patients who didn't follow post-operative instructions.
- Patients who are not able to come for the follow-up appointments.

Follow up:

- Patients who strictly follow post-operative instructions will perform another sleep study after 3 months from the day of the surgery.
- Percentage of AHI reduction will be calculated which in turn indicates post-surgical improvement.

2. Matching criteria and allocation ratio

The patients will be randomly allocated to the intervention groups using computer-generated random numbers that will be performed by the main investigator ([name]). The patients will be allocated in a ratio of 1:1 (35 patients in each group).

The two groups will be equally clinically examined before surgical procedures. Then the decision of which group will be scanned with CBCT and which won't will be taken according to the randomized numbers placed in opaque sealed envelopes. The number will be picked by the main investigator ([name]).

The main investigator will be responsible for the generation of allocation sequence and will assign the patients to the 2 intervention groups. The main investigator will also be responsible for patient enrolment.

C) Variables

1. Details about variables

- Mean AHI reduction percentage.
- Level of Collapse of the upper respiratory airway.
- The volume of the upper respiratory airway.

2. Data sources and management

- The level of the collapse of the upper respiratory airway will be determined by an expert ENT surgeon with DISE.
- Radiographic assessment will be performed using the iCAT FLX V17-Series CBCT machine (Imaging Science International, ISI, PA, USA). Quick scan imaging protocol of 16cm x 13cm Field Of View (FOV) (120 KV, 5 mA, 2 sec) and 0.3 mm voxel size.
- Participants are required to wear a protective lead apron during scanning. The position of the X-ray tube will be adjusted to minimize the extent of scanning and to ensure the lowest radiation dose as much as possible. To prevent motion artifacts, participants will be instructed not to move their head, body, tongue, and jaws during scanning.
- Raw DICOM data from CBCT scanning will be checked to evaluate whether there were any motion artifacts in images at coronal, horizontal, and sagittal planes.
- CBCT scans at both ends of inspiration and expiration will be analyzed using Invivo5 software.

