- For the second outcome, CBCT images will be interpreted by three oral and maxillofacial radiologists independently; blinded from demographic data of the patients, DISE findings, and the results of each other.
- Each radiologist will evaluate the CBCT images for assessment of the level of collapse and assessment of the secondary outcomes. One radiologist will assess all the outcomes twice with more than 1month interval. Intra-observer and inter-observer variability of CBCT findings will be evaluated.

3. Addressing potential sources of bias

No source of bias. CBCT images will be interpreted by three oral and maxillofacial radiologists independently blinded from demographic data of the patients, DISE findings, and the results of each other.

D) Study size

1. Study size

This study aims to assess surgical improvement in OSA patients after imaging of upper Respiratory Airway using CBCT and DISE using mean AHI reduction percentage. According to the results of (**Pang et al. 2020**), the mean of AHI reduction percentage and the minimal clinically important difference estimated by the expert was 21.6. By adopting an alpha (α) level of 0.05 (5%) and a power of 80%, the predicted sample size is 35 per group with a total of 70. To compensate for losses during follow up, the sample will be

increased by 20% to be 84 participants in total. Sample size calculation was achieved using PS: Power and Sample Size Calculation software Version 3.1.2 (Vanderbilt University, Nashville, Tennessee, USA).

E) Quantitative variables

1. Handling of quantitative variables in the analyses

The volume of the upper respiratory airway will be determined and correlated with its level of collapse.

F) Statistical methods

1. Statistical methods

Data will be analyzed using SPSS (statistical package for social sciences) version 22. Qualitative data will be presented as number and percent, Quantitative data will be tested for normality by the Kolmogorov-Smirnov test then described as mean and standard deviation for normally distributed data and median and range for non-normally distributed. The appropriate statistical test will be applied according to the data type with the following suggested tests: Chi-Square for the categorical variable. Student t-test and Mann Whitney U test for continuous variables.

II. Ethics and dissemination:

a. Research ethics approval

The study protocol will be submitted to the Ethics committee in the Faculty of Dentistry, Cairo University for approval.

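### The plan fixes no single test or effect estimate for percentage AHI reduction, the outcome that sizes the trial, and does not use the baseline AHI it collects to sharpen the comparison

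*Combined protocol and SAP*

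**What the plan says.** Section I.C.1 lists "Mean AHI reduction percentage" as the first variable. The Follow up part of I.B.1 takes it from a repeat sleep study 3 months after surgery: "Percentage of AHI reduction will be calculated which in turn indicates post-surgical improvement". Section I.D.1 sizes the trial on it: "the mean of AHI reduction percentage and the minimal clinically important difference estimated by the expert was 21.6", with alpha 0.05, 80% power and 35 patients per group.

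Section I.F.1 is the whole analysis plan. After a Kolmogorov-Smirnov test, quantitative data are "described as mean and standard deviation for normally distributed data and median and range for non-normally distributed". Then: "The appropriate statistical test will be applied according to the data type with the following suggested tests", which for continuous data are "Student t-test and Mann Whitney U test for continuous variables". No test is assigned to percentage AHI reduction, and no between-group difference, confidence interval or covariate is named.

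Pre-operative AHI is recorded by polysomnography and graded from mild (5-14) to severe (above 30) in I.A.1. On allocation, I.B.2 says: "The patients will be randomly allocated to the intervention groups using computer-generated random numbers". It mentions no stratification by severity.

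**The concern.** Two things are left open for the outcome that carries the trial.

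**The estimate.** Whether the result is a difference in means or a pair of medians is settled only once the data are seen. Only the first answers the question that the sample size was set for. Even if the data look normal, the plan promises group means and SDs, not a difference with its uncertainty.

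**The baseline.** Dividing by baseline AHI is not the same as adjusting for it. Unless 3-month AHI is strictly proportional to baseline, percentage reduction still depends on where a patient started. With 35 per arm and no stratification, a chance imbalance in severity can then move the result in favour of either arm.

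**Working it through.** **1. The plan's own figure.** No SD is given, so 35 per group cannot be checked forwards. Solving back with the normal approximation: SD = 21.6 / [(1.960 + 0.842) × √(2/35)] = 21.6 / 0.670 = 32.25. With the noncentral t it is 31.8 two-sided or 36.0 one-sided; sidedness is not stated. I use 31.8 unless noted.

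**2. A mean difference is not a median difference.** Assume AHI is log-normal, so the follow-up/baseline ratio is log-normal with log-SD τ in both arms. The ratio has mean m and median m × exp(−τ²/2), so a mean difference of 21.6 is a median difference of 21.6 × exp(−τ²/2). Setting the pooled SD to 31.8:

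| Control mean reduction | τ | Median difference |
|---|---|---|
| 40% | 0.58 | 18.3 |
| 50% | 0.69 | 17.0 |
| 60% | 0.85 | 15.1 |

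Nor does a significant rank test imply a difference in means. In an illustrative simulation with equal means (50%) and SDs of 45 and 15, rejection was 8% for the t-test and 41% for a rule that switches to Mann-Whitney when Kolmogorov-Smirnov rejects in either arm.

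**3. How baseline acts on percentage reduction.** A fixed fall of 5 events/hour is 5/5 = 100% at AHI 5, 5/15 = 33% at 15 and 5/30 = 17% at 30: a smaller percentage reduction at higher baseline. If instead log follow-up AHI rises with log baseline at a slope below 1, higher baselines show a larger percentage reduction. At a slope of exactly 1 there is no dependence.

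**4. Size of a chance imbalance.** The standardised baseline difference has standard error √(2/35) = 0.239. P(imbalance ≥ 0.3 SD) = 2 × P(Z > 0.3/0.239) = 2 × P(Z > 1.255) = 0.21. In those trials the mean imbalance is 0.239 × φ(1.255)/P(Z > 1.255) = 0.239 × 0.1815/0.1047 = 0.414 SD.

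**5. Its effect when CBCT does nothing.** Assumptions: log-normal AHI, mean reduction 40-60% in both arms, SD 31.8, log-scale correlation 0.3-0.7, and follow-up/baseline log-SD ratio 1.0 or 1.4. The slope is correlation × ratio, 0.3 to 0.98. These choices force a baseline log-SD s of about 0.3-0.9, and baseline is not cut off at AHI 5. The expected false difference is 100 × m × (1 − slope) × s × 0.414 points.

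- Slope 0.3, mean reduction 40% (m = 0.6, s = 0.42): 100 × 0.6 × 0.7 × 0.42 × 0.414 = 7.3 points.
- Slope 0.98, mean reduction 40% (m = 0.6, s = 0.50): 100 × 0.6 × 0.02 × 0.50 × 0.414 = 0.2 points.

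Simulation over 18 such scenarios agrees:

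| | Unadjusted t-test | ANCOVA on log baseline |
|---|---|---|
| Rejection, imbalanced trials | about 5-13% | about 4-5% |
| Mean false difference, imbalanced trials | about 0-7 points | 0.2 points or less |
| Rejection, all trials | about 5% | about 5% |

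**6. Precision and power at a true difference of 21.6.** The ANCOVA interval was 0.85 to 1.01 times as wide as the unadjusted one. Power changed by −0.7 to +10.5 points against the t-test and by −7.0 to +6.8 against the switching rule. These scenarios force a baseline log-SD of 0.40-1.09. The upper end is very wide: exp(2 × 1.96 × 1.09) is about a 72-fold spread for the central 95% of patients.

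**The case against.** **Adjustment is a preference.** Randomisation makes the unadjusted difference unbiased on average, and its type I error is about 5%. This stands. A reader might infer from the 13% figure that the planned test has an inflated error rate. It does not: 13% applies only within the 21% of trials with larger imbalances, and only at the lowest slope.

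**The mean may be reported anyway.** The variable is declared as a mean, and I.D.1 says that improvement is assessed by it. So it goes too far to say that non-normal data would certainly leave the mean unreported. The descriptive rule in I.F.1 conflicts with the declared variable without clearly overriding it. The step from the normality test to Mann-Whitney is also implied, not written. That leaves the analysis less settled, not more.

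**The rank test may do better.** With strong skew, Mann-Whitney can have more power than a comparison of means. This stands too, so power is not the argument here.

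**The simulations rest on invented distributions.** They do, because the documents give none. The absence of a named test and estimate needs no simulation.

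**Conclusion.** The point holds on the missing analysis. For the outcome that sizes the trial, the plan suggests tests but fixes none, names no between-group estimate or confidence interval, and leaves open a move to medians that cannot be compared with 21.6. That comparison depends on reading 21.6 as the between-group difference; the sentence in I.D.1 attaches it to the mean as well.

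Using baseline AHI would improve precision and protect against chance imbalance. The benefit runs from almost nothing (slope 0.98) to the removal of a false difference of about 7 points, roughly a third of 21.6 (slope 0.3). Where the real data lie is unknown. A reader might infer that imbalance always flatters the arm with the higher baseline. The documents do not support that, since the direction depends on how follow-up AHI relates to baseline. The trial is not invalid as planned, but its main result is not yet defined.

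**What to change.** Before any 3-month AHI is seen, replace the test list for this outcome with one primary analysis: ANCOVA (linear regression) of percentage AHI reduction on arm and log baseline AHI. Report the adjusted mean difference in percentage points with a 95% CI. Fix the standard error in advance, for example HC3, so that skew does not change the method. Do not use Kolmogorov-Smirnov to choose the test. Report Mann-Whitney as a sensitivity analysis whatever the data look like.

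No new data are needed, and the outcome and the 21.6 target stay as declared. The downsides are:

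- one degree of freedom;
- with HC3, a loss of 1.4-2.0 points of power against the t-test if percentage reduction is unrelated to baseline;
- HC3 interval coverage as low as 93.1% under strong skew;
- under strong skew, less power than the switching rule, which then mostly uses the rank test: up to 7.9 points less with HC3 at SD 31.8, and up to 11.9 points less with ordinary ANCOVA at SD 36.0.

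A team that does not want adjustment should still name one test and one mean difference with its confidence interval.
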